### **11.4 Inclusion of Minorities**

Potential study subjects will not be excluded from this study for reasons of race or gender and efforts will be made to enroll in representative numbers with respect to both gender and race. In particular, no racial discrimination will be made in subject enrollment. The participation of minority subjects will be actively encouraged throughout the study.

## **11.5 Study Modification/Discontinuation**

The study may be modified or discontinued at any time by the IRB (or Human Research Committee), the study sponsor, the Office for Human Research Protections (OHRP), or other government agencies as part of their duties to ensure that subjects are protected.

## **12 PUBLICATION OF RESEARCH FINDINGS**

[name] will be responsible for publications of results from this trial and will comply with NINDS guidelines on publication of NIH funded clinical trials. Her responsibilities will include the following:

- Analyze and interpret data gathered in this study, and write publications from these data.
- Submit manuscripts to selected journals and address peer reviewers' comments.
- Submit abstracts to selected meetings and present data at the meetings.
- Determine authorship on the basis of the Uniform Requirements for Manuscripts Submitted to Biomedical Journals (International Committee of Medical Journal Editors, 1997).

- 3) Quality of life as measured using the PROMIS SF v1.1 will be compared between the treatment groups using a shared-baseline linear mixed model for correlated, longitudinal assessments of PROMIS with fixed effects of time and the treatment x time interaction and age, gender, duration of disease and their interactions with time included as covariates and random participant specific intercepts and slopes.

Safety data will be summarized by treatment group. Total numbers of adverse events, categorized by organ system, will be compared between groups using negative binomial regression and the proportion of participants experiencing each type of event by Fisher's exact test.

Tolerability will be measured in two ways:

- 1) The amount of engagement that participants exhibited as measured by the number of interactions they had with a dietitian and the number of times that they interacted with the app,
- 2) The length of trial involvement as measured by the time to the last interaction with a dietitian (in-person or by App). Many participants were lost to follow-up (need to make sure documented). Participants who came to clinic visits only (seeing RD) but

did not engage otherwise, their last date of engagement is recorded in the Final Disposition form under "loss to follow-up"

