#### **Objectives and Endpoints**

##### **Primary Objectives**

To study the feasibility, safety, tolerability and efficacy to maintain or increase body weight of an e-Health application and in-person nutritional counseling compared to standard of care and to each other.

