### ***5.3 Monitoring of Weight***

Weight will be assessed at every clinic visit in all three groups. Participants in both intervention arms will be asked to weigh themselves at home or in a clinic or allied health professional office every 2-4 weeks and either enter their weights into the e-Health app or in to their Self-Weighing Log. Participants in the in-person arm will be instructed to report significant weight changes by phone to their clinic RD. The clinic RD may modify the dietary recommendations at any time based on observed weight loss, adverse events, or at their discretion. Persistent weight loss despite >90% dietary compliance will prompt an increase in target calories by 235 Kcal/day, or more if the weight loss is more than 0.5 kg/week. Changes in the dietary recommendations will be recorded in the EDC.

Any weight loss >1.5 kg during the study will prompt an increase in the frequency of telephone contact and an appropriate increase in the recommended caloric goals. In addition, any report of weight loss will prompt the treating dietitian to explore (by telephone) whether this is due to unwillingness to continue participation in the trial, inability to comply with the prescribed diet (due to weakness, dysphagia, or dependence on caregivers), or inadequate caloric recommendations. Reported dysphagia (using the swallow screening questionnaire, Appendix 9) will prompt the treating RD to refer the patient for an early in-person evaluation by their medical providers. Participants who lose more than 3 kg despite non-invasive attempts to maintain body weight will be referred to a Speech Language Pathologist for evaluation of dysphagia and possible consideration of a feeding tube.

All participants who require a feeding tube during the study will be prescribed enteral nutrition based upon results of the High Fat/High Calorie diet study. Jevity 1.5 will be prescribed at 1.5 times their calculated TDEE using the HB equation, adjusted for a self-reported activity factor [39]. Given the safety and tolerability results of this study, we do not feel that it is ethical to use a control or eucaloric diet in the standard care arm.

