#### **6.1.2 Telephone Visits (Every 2-4 weeks)**

The Research Coordinator on the study will contact all participants by telephone at month 1 in all arms to determine if there have been any adverse events. The Coordinator will also contact participants by telephone who are unable to return to the clinic for their routine clinic visits, in order to perform disease-related outcome measures and the quality of life questionnaire.

After the initial screening/baseline visit, the treating Registered Dietitian will monitor dietary intake and weight in the in-person arms every 2-4 weeks as necessary based upon observed weight changes. They will monitor dietary compliance by having participants complete paper food records and faxing them along with the Self-Weighing Log for review. They will then contact participants by telephone to query any weight loss or emergence of adverse events. If the treating RD identifies weight loss despite >90% compliance with dietary recommendations, they will adjust their dietary recommendations to meet the target weight from Table 2. They will then contact the study participant at least once every 2 weeks until the participant's weight has stabilized or increased. The frequency and duration of counseling sessions will be documented in the EDC.

The RD in the e-Health Application arm will contact participants who report weight loss through the App directly, through email, or by telephone if necessary. The RD will assess whether the weight loss is due to an inability to comply with the prescribed diet (due to weakness, dysphagia, or dependence on caregivers), versus inadequate caloric recommendations. Symptoms of dysphagia using the self-reported swallow screening questionnaire will prompt the treating RD to refer the patient to SLP for an early in-person evaluation.

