## **6.2 Definitions of Evaluations and Outcome Measures**

### **6.2.1 Primary Outcome Measures**

#### **6.2.1.1 Safety and Tolerability**

Safety will be evaluated using reporting of hospitalizations, deaths and other serious adverse events, and treatment discontinuations due to adverse events. Tolerability will be defined as the number of participants who do not decline nutritional counseling, i.e. the number of participants who complete the 6 months of counseling sessions in the in-person arm, or who enter at least 80% of the required data in the e-Health application arm. Tolerability will not be defined based on compliance with nutritional recommendations as compliance may be affected by other factors such as disease progression.

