### **9.1 *Safety and Tolerability***

All randomized subjects will be considered evaluable for tolerability and safety. Subjects lost to follow-up will be considered treatment failures at the time they drop out of the study. The data will be reviewed by the independent Medical Monitor, using the considerations here as guidelines. Their recommendation would then be reviewed by the Principal Investigator.

Safety data will be summarized by disease group and treatment group and reported to the independent Medical Monitor every 3 months during the study. Total numbers of adverse events will be compared within each disease group and among treatment groups using negative binomial regression and the proportion of participants experiencing each type of event by Fisher's exact test. Every 3 months the Medical Monitor will review cumulative study reports to determine if there has been an excess rate of serious adverse events in any of the arms. At two interim analyses, mortality rates will be compared, and one or both intervention arms may be terminated for one or more disease groups according to pre-determined stopping rules described below.

In the tolerability analyses, a subject will be regarded as a treatment success if he/she complies with at least 80% of the nutritional counseling sessions, or enters at least 80% of the required electronic data.

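### Tolerability, a primary outcome, is defined inconsistently: the SAP replaces the protocol's 80% success rule and its drop-outs-as-failures rule with contact counts that have no denominator and depend partly on weight loss

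*SAP*

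**What the plan says.** The Précis gives the primary objective as "To study the feasibility, safety, tolerability and efficacy to maintain or increase body weight", and Protocol 6.2.1.1 places tolerability under the primary outcome measures. Three definitions follow.

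- **Protocol 9.1** (and the Précis, Statistical Methods): a participant is a success "if he/she complies with at least 80% of the nutritional counseling sessions, or enters at least 80% of the required electronic data". Section 9.1 adds: "Subjects lost to follow-up will be considered treatment failures at the time they drop out of the study". Section 9.3, under treatment discontinuation, likewise treats those who discontinue as failures in this analysis.
- **Protocol 6.2.1.1:** 80% of required data in the e-Health arm, but "the number of participants who complete the 6 months of counseling sessions in the in-person arm". It also says that tolerability is not to rest on dietary compliance, because disease progression and other factors can affect compliance.
- **SAP, tolerability paragraph:** measure 1 is engagement "as measured by the number of interactions they had with a dietitian and the number of times that they interacted with the app". Measure 2 is length of involvement, taken as time to the last dietitian interaction. The SAP gives no threshold, denominator, success status or test for either.

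The frequency of dietitian contact is not fixed. Section 5.3 states: "Any weight loss >1.5 kg during the study will prompt an increase in the frequency of telephone contact". Section 6.1.2 sets in-person monitoring at every 2 to 4 weeks according to weight change. After weight loss despite more than 90% dietary compliance, the dietitian must "contact the study participant at least once every 2 weeks until" weight stabilises or rises. In the e-Health arm the dietitian contacts participants who report weight loss.

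**The concern.** The SAP should put the protocol's primary outcomes into operation. Here it swaps a binary success rule for counts and a duration, and it no longer says that a drop-out is a failure. The SAP is dated April 11, 2018, and the same paragraph already remarks that follow-up was lost for many participants, so the missing rule is one that would affect the result.

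The count also measures something other than tolerability. A participant's number of dietitian contacts depends on how many were called for, and that depends partly on weight. Without a denominator, more need for calls and more willingness to take them look the same. The two arms also generate different kinds of event in very different numbers. What is at stake is whether the reported tolerability result can be read as the outcome that the protocol promised.

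**Working it through.** The documents give no sample size, alpha or power for tolerability, so there is no stated figure to reproduce. The check sets the definitions side by side and then counts contacts.

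**1. Definitions**

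| Source | In-person | e-Health | Loss to follow-up or discontinuation |
|---|---|---|---|
| Protocol 9.1, 9.3 | at least 80% of sessions | at least 80% of entries | failure |
| Protocol 6.2.1.1 | completes 6 months of sessions | at least 80% of entries | not stated there |
| SAP | counts; time to last dietitian interaction | counts; time to last dietitian interaction | no failure rule |

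**2. Scale.** Inputs: 24 weeks (the period in Protocol 9.3); telephone contact every 2 to 4 weeks (6.1.2); 4 diet days and 2 weights per 2-week cycle (5.1.2).

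- In-person calls: 24/4 = 6 to 24/2 = 12.
- App entries: 24/2 = 12 cycles × (4 + 2) = 72. The 80% threshold is 0.8 × 72 = 57.6, so 58 entries.
- Ratio at full participation: 72/12 = 6 to 72/6 = 12.
- Over 26 weeks: 6.5 to 13 calls and 13 × 6 = 78 entries.

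**3. One participant against another.** This takes the 9.1 denominator as the contacts due for that participant. If w of the 24 weeks are on two-weekly contact and the rest on four-weekly, contacts due are N = (24 − w)/4 + w/2 = 6 + w/4.

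- w = 0: N = 6. Attending 6 of 6 is 100%, a success.
- w = 24: N = 12. Success needs 10, since 0.8 × 12 = 9.6. Attending 7, 8 or 9 (58%, 67%, 75%) is a failure, yet each count exceeds 6.
- w = 12: N = 9, and 0.8 × 9 = 7.2. Attending 7 of 9 (78%) is a failure, yet 7 exceeds 6.
- w = 8: N = 8, and 0.8 × 8 = 6.4. No count is both above 6 and below 80%, so this inversion disappears.

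**4. Groups (illustration; attendance and weight-loss shares are assumed).** Let a share f lose weight and be due 12 contacts throughout, let the rest be due 6, and let attendance be a. The mean count is 6a(1 − f) + 12af = 6a(1 + f). The success rate weights P(at least 5 of 6) and P(at least 10 of 12), both binomial, by 1 − f and f.

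| f | a | Mean count | Success under 9.1 |
|---|---|---|---|
| 20% | 90% | 6 × 0.9 × 1.2 = 6.48 | 89% |
| 50% | 90% | 6 × 0.9 × 1.5 = 8.10 | 89% |
| 50% | 80% | 6 × 0.8 × 1.5 = 7.20 | 61% |
| 70% | 70% | 6 × 0.7 × 1.7 = 7.14 | 30% |

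The count favours the group with lower attendance when its attendance, divided by the other group's, exceeds (1 + f of the other group)/(1 + f of its own). For 20% against 50% losing weight this is 1.2/1.5 = 0.80; for 20% against 40%, 1.2/1.4 = 0.86; for 20% against 70%, 1.2/1.7 = 0.71. Below those ratios the count and the success rate agree in direction.

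**The case against.** The case for the SAP is substantial on several points.

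- **Accepting more calls is not failing tolerability.** Section 6.2.1.1 separates tolerability from dietary compliance, and the two-weekly trigger in 6.1.2 applies to participants who are complying. This stands: a high count in someone losing weight is not a wrong answer in itself. But the count then partly reflects how many calls were needed, which is the kind of disease influence that 6.2.1.1 set out to avoid.
- **A compliant, weight-stable app user is not scored as disengaged.** One might infer this from the few dietitian contacts such a user would have. But measure 1 also counts app interactions, and full entry gives 72. Section 5.1.2 provides only for notifying the dietitian of missing data; it does not say that contact follows. App prompts are on a fixed two-week cycle, so the link between app entries and weight loss is weak.
- **The arms can be compared on measure 2.** Time to last dietitian interaction has the same unit in both arms and shows drop-out as a shorter duration. This stands, though it supplies no success criterion.
- **No between-arm test of tolerability is planned in the SAP.** This stands, so no wrong inference is built into the plan.
- **The 6.2.1.1 wording may mean staying in counseling, not attending every session.** This is a fair reading. On the strict reading, 12 sessions at an assumed 95% attendance give 0.95^12 = 54% completing all, against 98% reaching at least 10. Neither the attendance nor that reading is in the documents, so no weight is placed on those figures. The wording still differs from 9.1.
- **The protocol's in-person denominator is itself loose,** because 5.1.1 makes additional telephone counseling as-needed. This stands, and the fix must deal with it.

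**Conclusion.** The inconsistency is established from the text alone: one primary outcome, two protocol wordings for the in-person arm, and a SAP that uses neither and omits the failure rule for drop-outs.

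The weakness of measure 1 is also established in kind: it has no denominator, its dietitian component depends on weight change by protocol, and full participation produces counts 6 to 12 times apart between arms. Its effect on results is only possible. The 9-of-12 against 6-of-6 example needs two-weekly contact for all 24 weeks; with 12 weeks of it a milder inversion remains (7 of 9 against 6 of 6), and with 8 weeks there is none against 6 of 6. The group figures rest on assumed attendance and weight-loss shares.

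Two stronger conclusions are not supported. A reader might infer that the SAP endpoint will point the wrong way; the documents do not show that, and measure 2 is less exposed. A reader might also infer that the failure rule was dropped because of the drop-out seen; the SAP shows that drop-out was known when it was written, but gives no reason for the change.

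**What to change.** Make the Protocol 9.1 rule the tolerability endpoint in the SAP: the proportion in each intervention arm reaching at least 80% of required sessions or entries, with losses to follow-up and discontinuations counted as failures. Align the in-person wording of 6.2.1.1 to it, and state the denominators:

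- **e-Health:** 4 diet days and 2 weights per 2-week cycle, so 72 entries over 24 weeks with success at 58.
- **In-person:** a fixed minimum taken from the existing schedule, namely the baseline, month 3 and month 6 visits plus telephone contact at least every 4 weeks. That is 3 + 6 = 9 contacts (8 needed, since 0.8 × 9 = 7.2), or 3 + 4 = 7 (6 needed, since 0.8 × 7 = 5.6) if the visits stand in for the calls due at weeks 12 and 24. The SAP should say which.

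Cap attainment at 100% so that extra calls cannot raise the score. One consequence should be accepted openly: if visits are attended alike, the participants with 9 of 12 and 6 of 6 calls both reach the minimum, so extra calls no longer separate them. Report contact counts and time to last engagement as descriptive.

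The cost is SAP wording and one sentence in 6.2.1.1. Session frequency is already recorded in the EDC and entries in the app. A fixed denominator avoids needing a record of sessions offered and declined. Dates of loss to follow-up must be complete, which the SAP itself flags as still to be checked. The reported success rate may be lower. No change to contact practice or clinical management is proposed.
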